#### Anti-Stigma Intervention

Health care workers working at sites randomized to the anti-stigma only or the combination anti-stigma and resilience arm will receive anti-stigma training sessions to address issues with multiple stigmas that may be impacting their ability to provide quality care for PLHIV in Mozambique. The training will occur once every other week, for at least 4 sessions of 60-120 minutes each. The day and time of the intervention session will be determined by health facility staff to facilitate attendance.

Study personnel will work with health care workers at study sites to combine and adapt the most applicable components from three evidence-based anti-stigma interventions. These interventions were selected because: i) they were developed in low and middle income settings (and parts of one intervention have been tested in Mozambique through International Association of Providers of AIDS Care [IAPAC] modules), ii) their focus is on identifying HIV-related and other intersecting stigmas, the impact stigma has on patients, the impact stigmatized beliefs have on health care providers, and iii) they propose ways to create a stigma-free environment in the health setting (see **Table 3**).

**Table 3:** Adapted Anti-Stigma Sessions

Title of exercise/session	Intended learning outcomes
1. Naming stigma through pictures/defining stigma; describing the different types of stigma; consequences of stigma	
 
Participants discuss what similar stigma takes place in different contexts and start to share stories of what they have personally witnessed.
 
Recognition of how personal attitudes and beliefs influence stigmatizing behavior.
 
Helps participants to recognize the causes of stigma and how the resulting effects are manifested.
 
Interactive component: brainstorming as a group the types of and expressions of stigma in the workplace.
 

2. Communication skills with patients to avoid stigmatizing them	
 
Discussing and giving examples of stigmatizing communication with PLHIV.
 
Discussing and giving examples of non-stigmatizing communication with PLHIV.
 
Correlate stigmatizing communications and its consequences on the care of PLHIV.
 
Correlate non-stigmatizing communications and its consequences on the care of PLHIV.
 
Interactive component: in pairs, example case scenarios and practice communication styles.
 

3. Communication skills to improve relationship with patients in situations where you (the provider) are uncomfortable	
 
Participants discuss difficult situations for communication.
 
Participants discuss examples of stigmatizing and non-stigmatizing communication in situations where patients are complaining; in situations where patients are rude or dismissive; in situations where provider feels uncomfortable when attending patients' part of key population;
 
Interactive component: discuss as a group about questions and/or potential examples when the provider did not feel informed or knowing how to respond; examples of difficult interactions and options for how to respond in those situations.
 

4. Humanization session to facilitate better understanding of the challenges faced by patients.	
 
Getting skills on how to explore on a regular basis the challenges faced by patients and how to strengthen the patient to overcome some of these challenges;
 
Interactive component: example case scenarios and ask group to offer possible factors that influenced the 'why' of that situation to practice empathetic thinking and compassion skills for patients' experiences.
 

## **Procedures for Health Care Workers**

### Survey Data Collection (Objectives 1 and 3)

All health care workers who agree to enroll in the study will be asked to complete study questionnaires i) at baseline, ii) within 1 month after last session (or 6 months after enrollment in the control site), and iii) approximately 10-11 months after enrollment. Sociodemographic data will be collected within the baseline survey. We will measure HCW attitudes (n=100) towards their patients (stigma), as well as factors associated with well-being, including resilience, burnout, depersonalization, moral injury, depression (endline only), anxiety (endline only), and the Suicide Screening (endline only) (see **Table 4**; see **Appendix 1** for each measure). Details on the co-primary outcomes are noted below.

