### **Table 4: Measures (HCW)**

*Measures collected via surveys with HCW at baseline, and 1 month after the last session (6 months after baseline in the control site):*

- (1) Resilience
- (2) HIV Stigma
- (4) Burnout
- (5) Depersonalization
- (6) Moral Injury Questionnaire\*70
- (7) Depression #
- (8) Anxiety#
- (9) Suicide Screening#

*[\*Only to be done at baseline  
#Only to be done at endline]*

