## **Procedures for Patients living with HIV**

### *Procedures for PLHIV who have agreed to participate in the survey.*

Survey administration with PLHIV participants enrolled in the study will be completed at two time points: one at baseline (i.e., study initiation) and one at endline (i.e., at 6-7 months after study initiation), including sociodemographic data and three questionnaire components related to: Medical Mistrust, Patient Satisfaction, and Perceived stigma from Health care Providers (**Appendix 2**). The survey will be done at the health facility or at a location suggested by the participant as per the participant's preference, at a location where privacy can be guaranteed as much as possible with the support from a surveyor who is fluent in Echuabo (local language). Participants may be recruited for more than one survey time point, however, different PLHIV participants can be recruited at the two time points. Participants will be requested to allow the use of the Moral Trauma Protocol, Version 1.3; PI: [name], 27 September 2024

of a subset of data related to their ART medication pick-up history for the past 6 months will be collected from their medical records for use in analyzing the survey data (**Appendix 10**). These data will be extracted from the electronic patient tracking system OpenMRS™, which stores clinical information from the medical records of PLHIV registered at the health facility.

*Procedures for PLHIV for whom we will collect routine clinical data.*

We intend to collect demographic and clinical data from patients' medical records that include, but are not limited to: HF, NID, age, sex, level of education, marital status at enrollment in HIV care, date of enrollment in HIV care, date of ART initiation, ARV, Body mass index (BMI), CD4+ T-cell count, HIV-1 viral load (VL) (data and value), WHO clinical stage at the first visit and ART initiation, hemoglobin and full blood count on the date of enrollment in HIV care (or nearest), residence (urban or rural), and records of ART pick-ups (to assess retention) (**Appendix 9**). Data will be extracted from the electronic patient tracking system OpenMRS, that stores clinical information from the medical records of PLHIV registered at the health facility.

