## **Data Analysis**

### **Objective 1:**

#### Quantitative Data Analysis

We will first conduct descriptive analyses. Our psychological and psychosocial measures are continuous or pseudo-continuous (e.g., sums of Likert-style questions) variables. Our outcomes

will be changes in psychosocial measures from baseline to follow-up. Descriptive analyses will include boxplots and summary measures by intervention arm (4 groups). Our formal analyses (those that test hypotheses) will take advantage of the factorial nature of this pilot cluster randomized control trial. These analyses will group together sites as receiving resilience intervention (yes vs. no) and receiving anti-stigma intervention (yes vs. no); therefore, results from two sites will be compared with results from two other sites. This gives us a larger sample size for each comparison and allows us to fit linear mixed effects models that include random effects to account for the correlation between measurements taken from participants at the same site while ensuring that the fixed effect of the intervention is identifiable. We will report results from models that are unadjusted and adjusted for a small number of HCW-level baseline covariates (age, sex, HCW role, and baseline measures of the outcome). Model diagnostics will be performed and outcome variables will be transformed, if necessary, to meet model assumptions.

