## 15. Timeline

Time (month)	Activities/Description
Month 1	Recruit health care workers from four health facilities (n=100).

Month 1	Among HCW , assess baseline measures of (1) Resilience (2) Stigma (3) Burnout (4) Depersonalization (5) Moral Injury Questionnaire		
Months 1-4	Resilience/Wellness Intervention arm sessions; held bi-monthly	Resilience/Wellness and anti-stigma arm sessions, held bi-monthly	Anti-stigma arm intervention only sessions; held bi-monthly
Months 1-2 & Months 6-7	Recruit a sub-group of PLHIV patients receiving any HIV care and treatment into the study at the four study sites (total n=320) to assess impact of the interventions on medical mistrust, patient satisfaction, and perceived stigma from health care providers via baseline (study start) and end-line (approximately 6 months after study start) surveys.		
Months 1-12	Collect routine clinical data (retention, viral load) from all patients enrolled in care and treatment at the four study sites (n estimated approximately to be 16,000).		
Months 5-7	Among HCW , collect post-intervention surveys (repeat same measures as used at baseline, except for #5 Moral Injury Questionnaire) at all sites (control and intervention).		
Months 8-9	Recruit a sub-group of HCW participants at the three intervention sites for in-depth interviews related to moral injury/ moral trauma.		
Months 8-14	Conduct data analysis of survey outcomes among PLHIV and HCW.		
Months 10-11	Conduct surveys to assess depression, anxiety, and suicidality		
Months 12-15	Conduct data analysis of clinical outcomes among PLHIV.		
Months 12-18	Disseminate findings via community meetings with community members and clinicians		

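### The second health care worker survey follows a last-session clock at the three intervention sites but a 6-month clock at the control site, so control is followed 1 to 3 months longer

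*Combined protocol and SAP*

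**What the plan says.** Section 8.a, Survey Data Collection, schedules the second survey "within 1 month after last session (or 6 months after enrollment in the control site". Table 4 gives nearly the same rule: "1 month after the last session (6 months after baseline in the control site". Neither place gives a reason for the two clocks.

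Section 15 (Timeline) supplies the calendar limits:
- Month 1: "Recruit health care workers from four health facilities (n=100", and in the same month "assess baseline measures of (1) Resilience (2) Stigma (3) Burnout" and the other baseline measures.
- Months 1-4: sessions in all three intervention arms, for example "Resilience/Wellness and anti-stigma arm sessions, held bi-monthly".
- Months 5-7: "collect post-intervention surveys (repeat same measures as used at baseline, except for #5 Moral Injury Questionnaire) at all sites (control and intervention".
- Months 10-11: depression, anxiety and suicidality only. Resilience and stigma are therefore measured after baseline only at the second survey.

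Section 10 (Objective 1, Quantitative Data Analysis) says that the outcomes "will be changes in psychosocial measures from baseline to follow-up". Two sites are compared with two others for each intervention. The adjusted model uses age, sex, role and the baseline score, and the time between the two surveys is not among the terms.

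The patient survey uses one clock for every site: "one at endline (i.e., at 6-7 months after study initiation".

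**The concern.** A change score mixes any training effect with whatever would have happened over the interval anyway. A comparison between arms removes the second part only if the arms are followed for the same time. Here the control site is followed longer by rule. If resilience or stigma scores drift for any reason unrelated to training, control has more time to drift, and the difference enters the estimated effect. The control site is in the comparison group of both factorial contrasts, so this one scheduling choice touches both co-primary results. The descriptive four-arm summaries carry the whole gap.

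The analysis cannot readily repair this. If the three intervention sites share timing, site-level elapsed time takes one value at control and another at the other three sites. It is then the same variable as being the control site. With four sites, an intercept, two main effects and such a time term use up all the site-level information, and time cannot be told apart from the interaction. Spread in survey dates within sites might carry some information, but no such term is planned.

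**Working it through.** **The plan's own figure.** Section 7.c gives 1.07 SD detectable at 80% power with 25 workers per site, ICC 0.10 and two-sided 5%.
- Design effect: 1 + (25 − 1) × 0.10 = 3.4.
- Effective size for 50 versus 50: 50 / 3.4 = 14.7 per group.
- A two-sample t calculation (noncentral t) on that size gives 1.071 SD. The same method gives 0.850 SD at ICC 0.05 and 1.264 SD at ICC 0.15, against the stated 0.85 and 1.26. The figures reproduce and are not in dispute.

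**Length of follow-up.** Let Month k be the interval from k − 1 to k, in months.
- Baseline date b lies between 0 and 1.
- Last session L is at most 4. The intervention survey is at L + d, with d between 0 and 1, so no later than 5. The Months 5-7 row means no earlier than 4.
- The intervention survey therefore falls at 4 to 5, which is Month 5. The control survey is at b + 6, between 6 and 7, which is Month 7. The two do not overlap.
- Intervention interval, (L + d) − b: from 4 − 1 = 3 to 5 − 0 = 5 months. Control interval: 6 months.
- Gap: 6 − 5 = 1 month to 6 − 3 = 3 months. Table 4's reading (d = 1) gives the same range, with L between 3 and 4.

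**Share carried by a main effect.** For resilience, with t the interval at each site: (t_control + t_stigma)/2 − (t_resilience + t_both)/2. The anti-stigma contrast has the same form.
- Common intervention time t: (6 − t)/2, which is 0.5 month at t = 5 and 1.5 months at t = 3.
- Sites free to differ between 3 and 5: from (6 + 3)/2 − (5 + 5)/2 = −0.5 to (6 + 5)/2 − (3 + 3)/2 = 2.5 months.

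**What that could mean for the estimate.** The drift rate is an assumption: 0 to 0.10 SD per month, linear, in either direction. Under common timing:
- Bias: at most 1.5 × 0.10 = 0.15 SD. At the 1-month gap it is at most 0.5 × 0.10 = 0.05 SD.
- Against the detectable difference: 0.15 / 1.07 = 14%.
- Standard error of a two-versus-two difference: √(2 × 3.4 / 50) = 0.369 SD; 0.15 / 0.369 = 0.41.
- Type I error of a nominal 5% two-sided test with that shift: P(Z > 1.96 − 0.41) + P(Z < −1.96 − 0.41) ≈ 0.060 + 0.009 = 6.9%.

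With unequal intervention timing, the same drift gives at most 2.5 × 0.10 = 0.25 SD in one contrast; other combinations give close to zero.

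**The case against.** **The effect is small for a pilot of this kind.** No document suggests that either score drifts, and Section 12 already concedes that four sites is a severe limit. This stands as far as grading goes. But that limit concerns the number of clusters; unequal follow-up is a separate matter that scheduling removes at the same sample size.

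**The Months 5-7 window covers all sites.** It permits equal intervals but does not require them. Surveying intervention sites in Months 6-7 would break the last-session rule in Section 8.a.

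**Measuring soon after training is a sound choice, and 6 months matches the study period in the worker eligibility criteria.** Both are fair. They justify the intervention-site rule and explain where the control rule may come from, but not the difference between them. The patient survey is only a weak precedent, because patients attend no sessions.

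**Common timing is not assured.** This stands. The combined arm receives both courses and their sequencing is not stated. Half the gap is a conditional result, not a general one.

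**Stronger readings that the documents do not support.** A reader might infer a gap of 3.6-4.6 months, since four fortnightly sessions starting at enrollment span only 42 days. That survey would fall before the Months 5-7 row, so it does not keep every rule. A reader might also infer that the session schedule contradicts the timeline. It need not: a fortnightly course that ends late in Month 4 fits all the relevant sections.

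**Conclusion.** The concern holds. Followed as written, the plan gives the control site 1-3 months more follow-up than the intervention sites on both co-primary outcomes, with nothing in the analysis to account for it. The gap rests on all the calendar limits in Section 15 and the one-month rule being kept. The 0.15 SD ceiling rests on the assumed drift rate and on common timing across the three intervention sites. Without common timing, the imbalance in a given main effect could be smaller or larger.

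It would be tempting to say that the co-primary results are biased, or that the stated power is wrong. Neither follows. The documents give no drift rate, so size and direction are unknown, and the power figures reproduce. This is a low-cost improvement, not a fault that invalidates the trial.

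**What to change.** Keep the intervention-site rule. In Section 8.a and Table 4, replace the control site's 6-month rule with a survey in the same calendar weeks as the intervention sites' post-training surveys, and so at about the same time since baseline. Narrow the Months 5-7 row in Section 15 to match. Report the interval from baseline to second survey (median and range) by site beside the co-primary results.

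One fixed elapsed time for all four sites would be a worse remedy. If the combined arm ran its two fortnightly courses in sequence, eight sessions would end at week 14 against week 6 for a four-session site starting at the same time. A common survey date would then break the one-month rule and make time since training differ by arm.

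The cost is wording and scheduling, with no extra surveys. There would be no 6-month control value, and the control survey might no longer share a visit with the Months 6-7 patient survey. Baseline dates can still differ within Month 1, and if intervention sites finish at different times some difference between those sites remains. The reported intervals would show both.

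Appendix 4 already reports moral injury, which is measured only at baseline, so baseline data existed when this version was written. If the second surveys are also complete, only the interval reporting and a qualification of the co-primary results apply. The possible bias is then disclosed, not removed.

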### Qualitative Interview Data Collection (Objective 1)

We will conduct in-depth interviews with a maximum of 40 HCW within 1 month of the intervention completion. Qualitative interviews will focus on assessing factors associated with reach (who felt included/excluded; did subsets of groups drop-out?), effectiveness (perception of intervention success including changes in feelings towards patients, strategies adopted to improve wellness and resilience, experiences interacting with patients), adoption (facility- or provider-level barriers to adoption), implementation (capacity, adaptations necessary), and maintenance (barriers to sustainability, champions for sustainability).

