**There are six specific study questions:**

**Question 1:** Does our resilience/wellness intervention improve health care worker mental health outcomes?

**Question 2:** Does our anti-stigma intervention reduce stigma towards patients?

**Question 3:** Do health care workers who receive these interventions have suggestions about how they could be improved?

**Question 4:** Do our interventional trainings have any impact on patient adherence to HIV treatment?

**Question 5:** Do HCW in this area experience or have risk for moral injury/ moral trauma, and what services/interventions do HCW think could be supportive if experiencing this?

**Question 6:** Do HCW in this area experience depression, anxiety or suicidal ideation?

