**e. Participant recruitment, retention, and withdrawal:**

1. For Objectives 1 - 3:

Recruitment:

Health care workers (intervention, survey, in-depth interviews): The study team will perform information sessions at the health facility to explain the study. We will request to the head clinician that all health care workers attend to ensure everyone has a chance to learn about the project. If the health care worker is interested in participating, their informed consent will be obtained by a study assistant at the health facility or in a location of their preference. For the intervention and survey, we will recruit at convenience, and enroll all interested and eligible participants. For the in-depth interviews (Objective 1) that will be conducted within one month of the completion of sessions, we will attempt to enroll an equal number of HCW by facility and sector, so we will use purposive sampling to select individuals we believe can add varying views to the study findings. Health care workers can withdraw at any time without impact on their clinical position. For the in-depth interviews (Objective 3) related specifically to HCWs' perspectives and experiences of moral injury/ moral trauma, we will contact HCW who had consented to enrollment in the study at intervention sites. For the depression/anxiety surveys that will occur approximately 10-11 months after the intervention, we will also contact HCW who consented to be enrolled at both intervention and control sites and will re-consent HCW. We will inform them of the opportunity to participate in one additional interview or survey and explain the objective of this interview. If the HCW is interested in participating, their informed consent will be obtained by a study assistant at the health facility or in a location of their preference. For this interview with a sub-set of the intervention participant population, we will attempt to enroll an equal number/ proportion of HCW by sex, by health facility, and by category/clinical role of HCW, using purposive sampling to select individuals

we believe can add varying views to the study findings. These HCW can withdraw at any time without impact on their professional position.

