## Appendix 3: Interview Guides for Health Care Workers Who Participated in the Interventions (Objective 1)

### **Demographic information**

Age

Sex

Marital status

Education level

Academic training (*all levels achieved*)

Job position

Sector of work activity (in HF)

Community/province where born

Health care facility currently employed

Fluent in local language?

Family living with you in Zambézia (partner, children)?

Length of time you have been a health care worker?

Length of time you have been a health care worker at this health facility?

In addition to this HF, have you worked in particular in private clinics?

Are you a student in addition to working?

How many hours do you work per week (< 40 hours, 40 hours, > 40 hours a week)?

Do you have any close relatives living with HIV?

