### **In-depth Interview Questions**

1. Can you tell me about your experience attending the program? [specific which one depending on their site]

2. Think back to when you first hear about the program. Why did you decide to participate? What expectations did you have for the program when you first heard about it?

3. Now think about the program after you have participated. Did the program meet your expectations? If so, tell me ways that the program met your expectations.

- a) What was good about the program? (What did you like about the program?)
- 4. Tell me ways the program did not meet your expectations? Are there any other expectations you had from the sessions that were not met?
  - a) In what ways did the program fail to succeed?
- 5. Can you tell me if the program changed the way you think or interact with colleagues or patients at work?
- 6. Can you tell me ways we could improve the program? [Probe: topic areas to cover, ways to deliver support, group vs individual setting]
- 7. Is there anything we could do to advocate for health care providers at the provincial or national level in order to improve their wellbeing?
  - a) What do you need to be successful (in general and at work)?
  - b) What do you need to improve your wellbeing?

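### The Objective 1 interviews, meant for trained staff, can precede the post-training co-primary survey; the protocol should put the survey first

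*Combined protocol and SAP*

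**What the plan says.** **Interviews.** Section 8.a (Qualitative Interview Data Collection, Objective 1) says: "We will conduct in-depth interviews with a maximum of 40 HCW within 1 month of the intervention completion". Section 7.e gives the same window and makes selection purposive: "we will attempt to enroll an equal number of HCW by facility and sector". That sentence does not itself exclude the control site. However, Appendix 3 is titled for workers who took part in the interventions, its first question is about attending the programme, and study question 3 in Section 6 asks: "Do health care workers who receive these interventions have suggestions about how they could be improved". No guide is provided for untrained staff.

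**Interview content.** The effectiveness topic in Section 8.a covers "perception of intervention success including changes in feelings towards patients, strategies adopted to improve wellness and resilience". Appendix 3 asks: "Can you tell me if the program changed the way you think or interact with colleagues or patients at work".

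**Post-training survey.** Its timing is stated in three ways.
- Section 8.a (Survey Data Collection): at some point in the month following the last session, or six months after enrolment at the control site.
- Table 4 heading: "Measures collected via surveys with HCW at baseline, and 1 month after the last session", with the control site at six months after baseline.
- Section 15 (Timeline): in Months 5-7 the team is to "collect post-intervention surveys (repeat same measures as used at baseline, except for #5 Moral Injury Questionnaire) at all sites". Training sessions occupy Months 1-4. The Objective 1 interviews have no row.

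**Analysis.** Section 10 defines the outcomes as changes in score from baseline and tests each intervention factorially, two sites against two.

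**The concern.** Resilience and HIV stigma are co-primary outcomes, both self-reported by staff who know whether they were trained. Suppose a trained worker first spends an interview with study personnel discussing whether the programme changed how they see patients, and then fills in the resilience and stigma scales. The answers may reflect the interview as well as the training: the worker has had an extra occasion to reflect, and may wish to be consistent with what was said.

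Control staff have no matching contact, so any such shift enters the comparison as if it were part of the training effect. Nothing in the plan requires the survey to come first or provides for recording the order, and interview exposure is not among the adjustment covariates in Section 10 (age, sex, role and baseline score).

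**Working it through.** **1. Which contact comes first?** Let the last session be day 0. The interview falls within the following month.

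| Source for survey timing | Survey window | Order |
|---|---|---|
| Table 4 | at one month | interview first |
| Timeline | Months 5-7, training in Months 1-4 | interview often first |
| Section 8.a survey text | within the same month | either order |

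On the Timeline, if training ends by the close of Month 3, the interview window shuts before surveys open in Month 5. If training ends at the close of Month 4, the interview window runs through Month 5 and overlaps only the first of the three survey months.

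**2. The plan's own benchmark.** Section 7.c gives a detectable difference of 1.07 SD (25 staff per site, ICC 0.10, two-sided 0.05, 80% power).
- Design effect = 1 + (25 − 1) × 0.10 = 3.4.
- Effective n per group = 50 / 3.4 = 14.71.
- A two-sample t-test (noncentral t, df = 2 × 14.71 − 2) gives 1.071 SD.
- The same method gives 0.850 SD at ICC 0.05 and 1.264 SD at ICC 0.15, against the stated 0.85 and 1.26.

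The stated figures are reproduced.

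**3. Share of staff exposed.** The document inputs are at most 40 interviews and at most 25 staff per site. I assume that all 40 interviews are at the three trained sites, spread equally, and all before the survey.
- Per trained site: 40 / 3 = 13.3 of 25, or 53%. Control site: 0%.
- Each factor's yes group (two trained sites): 26.7 / 50 = 0.533.
- Each factor's no group (one trained site plus control): 13.3 / 50 = 0.267.
- Net imbalance: 0.533 − 0.267 = 0.267.

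**4. Illustrative bias.** If an interview held first shifts a score by d SD, the factorial contrast moves by (net imbalance) × d. The documents give no value for d; 0.2 to 0.5 is assumed.

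| Interviews held before the survey | Net imbalance | d = 0.2 | d = 0.5 |
|---|---|---|---|
| 20 | 0.133 | 0.027 SD | 0.067 SD |
| 30 | 0.200 | 0.040 SD | 0.100 SD |
| 40 | 0.267 | 0.053 SD | 0.133 SD |

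With 40 interviews first, the bias is 0.053 / 1.07 = 5% to 0.133 / 1.07 = 12% of the detectable difference. Under the effective-n t-test of step 2, a bias in either direction takes the two-sided type I error from 0.05 to between 0.052 and 0.064. If every survey comes first, the bias is zero.

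A single trained site against control would carry 0.533 × d, or 0.11 to 0.27 SD. That comparison is descriptive in Section 10, not the formal test.

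**The case against.** A reader might infer that the interviews always fall just before the survey. The documents do not support that: under the survey text in Section 8.a the two windows are the same month, and the survey may well come first.

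A reader might also infer that the interviews push scores in favour of training. That is not supported either. Besides asking what was good, Appendix 3 asks how the programme fell short of expectations, how it failed and how to improve it. Its question about change is neutrally worded, and much of the topic list in Section 8.a concerns reach, adoption, implementation and maintenance. The direction of any shift is therefore open.

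The size is also open. The per-person shift is assumed, 40 is a maximum, and the transcription line in the Section 14 budget has 30 units. Even the full illustration is small beside 1.07 SD. One interview adds little to four or more group sessions of 60 to 120 minutes that control staff do not receive, and Section 12 acknowledges the limits of a four-site pilot. All of this stands, and it keeps the point modest.

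It can also be said that at least 35 of 75 trained staff (75 − 40) are not interviewed, so the two groups could be compared. This helps less. Interviewees are chosen purposively, so a difference between them and their colleagues would mix selection with any interview effect.

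Finally, 1.07 SD is what the trial could detect, not the effect it expects. Section 12 says the data will inform a larger trial, and there an avoidable error of about 0.1 SD in an estimate is worth removing.

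**Conclusion.** The point holds as an avoidable gap in scheduling, not as a demonstrated bias. The Objective 1 interviews can precede the co-primary survey: they do so under Table 4, often under the Timeline, and possibly under Section 8.a. They touch the constructs being measured and are designed for trained staff only.

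The illustrative effect on the factorial contrast is 0.05 to 0.13 SD. It rests on three assumptions: 40 interviews spread equally over the trained sites, all of them before the survey, and a shift of 0.2 to 0.5 SD per interview. Fewer interviews, or fewer held first, reduce it in proportion. Neither size nor direction can be established from the documents. The case for acting is that the remedy costs almost nothing and that later analysis could not cleanly undo the effect.

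**What to change.** - In Section 7.e and in the Objective 1 interview paragraph of Section 8.a, state that each worker completes the post-training survey before the Objective 1 interview.
- Record the date of both contacts for each worker, so that the order can be verified and any departures reported.
- Reconcile the survey timing in Section 8.a, Table 4 and the Section 15 Timeline. A Timeline row for the Objective 1 interviews would make the order visible. The Timeline already places the Objective 3 interviews (Months 8-9) after the post-training survey (Months 5-7).
- Extend the interview window only if the reconciled survey date requires it. If the survey may fall at any time within the month, both contacts fit in the existing window. If it is fixed at one month, the interviews need a later limit.

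Cost: no change in sample size and no extra visit. Interviews may be slightly later, with slightly longer recall of the sessions.
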